Alpha-1 Antitrypsin (AAT) Enhances Islet Autograft Survival

Clinical Study protocol

Grant #: R01DK105183

Study sponsor: NIH/NIDDK

IND Number: Waiver given by FDA

MUSC IRB Number: Pro00053906 (version 3)

Activation Date: 12/01/2015

Last Protocol Update 05/14/2020

Accrual Objective: 48

Investigational Product: Prolastin C (Alpha-1 antitrypsin, AAT)

Objectives/endpoints: To describe and compare the safety and efficacy of treatment with AAT in chronic pancreatitis patients who undergo total pancreatectomy and islet autotransplantation (TP-IAT).

Study Design: Prospective, randomized, double-blind single-center trial to assess the effects of AAT or placebo in 48 adult chronic pancreatitis patients who undergo total pancreatectomy and islet autotransplantation.

Treatment Description: Randomly selected chronic pancreatitis patients with TP-IAT will receive intravenous infusion of AAT at 60mg/kg/week or placebo weekly for 4 weeks during the peri-transplant period.

Table of Contents

AAT in islet autotransplantation

1. Protocol Synopsis.....	5-6
1.1. Abbreviations.....	7
1.2. Study Definitions.....	8
2. Background and Rationale.....	9-12
2.1. Background.....	9-10
2.1.1.TP-IAT.....	9-10
2.1.2. Alpha-1 antitrypsin.....	9
2.1.3.Clinical trials use of AAT for Diseases.....	10
2.2. Rationale:.....	10-12
2.2.1.Rationale for selection of patient population.....	10
2.2.2.Rationale for the selection of dosing regimen.....	10
2.2.3.Rationale for the selection of administration and infusion rate.....	11
2.2.4.Known and potential risks and benefits to human participants.....	11
2.2.5.General risks.....	11
2.2.6.Risks of use of Investigation product.....	11
2.2.7.Risks of blood sampling.....	12
2.2.8.Other study-related procedures.....	12
2.3. Potential benefits.....	12
2.3.1.Benefits to TP-IAT patients.....	12
2.3.2.Benefits to society.....	12
3. Overall study design and plan description.....	13-15
3.1. Study design.....	13
3.2. Study time table	13
3.3. End of study.....	13
3.4. Study objective	13
3.5. Study endpoints	13
3.5.1. Primary endpoints	13
3.5.2. Secondary endpoints	14
3.5.3. Exploratory endpoints	14
3.5.4. Safety endpoints	14
3.5.5. Pharmacokinetics endpoints	15
4. Study population.....	16
4.1. Inclusion criteria	16
4.2. Exclusion criteria.....	16
4.3. Assignment of patient number.....	16
5. Investigational product	17-19

5.1. Investigational Product	17-19
5.1.1. Prolastin-C	17
5.1.2. Placebo	17

1.1. PROTOCOL SYNOPOSIS

Study Sponsor	NIH/NIDDK	
Investigational Product	Alpha-1 antitrypsin (AAT)	
Indication	Patients with chronic pancreatitis	
Title of Study	AAT Enhances Islet Autograft Survival	
Protocol Date	12/01/15	

OBJECTIVES

Primary objective: To describe and compare the safety and efficacy of treatment with AAT in chronic pancreatitis patients who undergo total pancreatectomy and islet autotransplantation (TP-IAT).

METHODOLOGY

Study Design	Prospective, controlled, double-blind
Treatments	Recipients will receive AAT before and post islet transplantation
Treatment Duration	Recipients will receive a total of 4 weekly infusions of AAT or placebo.
Study Drug and Formulation	Prolastin-C (Grifols)
Dose and Route of Administration	
 • AAT 60 mg/kg (IV) • Placebo- 0.9 % sodium chloride (IV). 
The first dose will be given on the day of islet transplantation before total pancreatectomy (D0), and then on days 7, 14, and 21 days of islet transplantation.

Number Planned	48
Major Inclusion Criteria	
 • Patients scheduled for total pancreatectomy and islet autotransplantation • Age > 18 years • Diabetes free before surgery

Exclusion Criteria	
 • Patients who are under immunosuppression • Patients who have had puestow or frey pancreatic surgery • Patients who have Immunoglobulin A (IgA) deficiency, known antibodies against IgA, or individuals with a history of severe immediate hypersensitivity reactions, including anaphylaxis to Alpha₁-proteinase inhibitor products (allergic to AAT)
Safety	
 • Physical examination, hematology, serum chemistry, urinalysis, vital signs, adverse event (AE) monitoring, and concomitant medications.
Efficacy	Efficacy of AAT therapy during peri-transplant period in chronic pancreatitis patients who undergo TP-IAT as assessed through islet function, onset of diabetes, glycemic control, pain relief and quality of life measurements.
ENDPOINTS	
Primary Endpoint	Area under the curve for the serum C-peptide level during the first 4 hours of an mixed meal tolerance test (MMTT), normalized by the number of islet equivalents (IEQ)/kg at day 365±14 after the transplant.
Secondary Endpoints	
 • Proportion of insulin-independent patients following IAT • Average daily insulin requirement. • β cell function as assessed by β-score. • Quality of life as measured by SF-12 questionnaire. 
Measurements will be performed at 365±14 days post-transplantation.

Exploratory Endpoints	
 • Measurements of primary and secondary endpoints at 75±14 day • Immediate blood mediated inflammatory response • Expression of chemokines/cytokines expression in serum • Genomic DNA analysis • RNAseq analysis of gene expression profiles in peripheral blood mononuclear cells post transplantation
STATISTICAL METHODS AND ANALYSIS	

1.2. Abbreviations:

AAT:	Alpha-1 antitrypsin
AE	Adverse Event
CP:	Chronic pancreatitis
CRF:	Case report form
CP:	Chronic pancreatitis
CFR:	Code of Federal Regulations
cGMP:	Current good manufacture practices
CRF	Case Report Form
CTCAE	Common Terminology Criteria for Advance Event
DSMB	Data and Safety Monitoring Board
GLMM	Generalized Linear Mixed Model
HbA1c:	Glycosylated hemoglobin
HR-QOL	Health-Related Quality of Life
LOCF	Last Observation Carried Forward
IEQ:	Islet equivalent number
IBMIR:	Immediate blood mediated inflammatory response
IV:	intravenously
Kg:	Kilogram
MMTT:	Mixed meal tolerance test
mITT	Modified Intention-to-Treat
MSM	Medical Safety Monitor
PAG	Physician's Global Assessment
PBMCs:	Peripheral blood mononuclear cells
PP	Per-Protocol
QOL:	Quality of Life
SAE:	Serious Adverse Event
SOC	Standard of Care
SP	Safety Population
T1D:	Type 1 diabetes
TP-IAT	Total Pancreatectomy and Islet Autotransplantation

1.3. Study Definitions:

Insulin-independence: is defined as free of exogenous insulin for 14 or more consecutive days, with adequate glycemic control as defined by: (1) A glycated hemoglobin (HbA1c) level < 6.5%, (2) Fasting blood glucose < 126 mg/dl more than 3 times in the past week based on a minimum of once daily measurement. (3) 2-hour post-prandial blood glucose does not exceed 180mg/dl more than 4 times in the past week, (4) A laboratory fasting glucose in the non-diabetic range (< 126 mg/dl), and at least one MMTT fasting or stimulated c-peptide $\geq 0.5\text{ng/ml}$

Insulin dependent: Subjects who do not meet the criteria for insulin independent.

Adverse events (AE): According to the International Conference on Harmonization (ICH) Guidelines (Federal Register.1999;60 (40):11285), an AE is defined as follows: An AE is any untoward medical occurrence in a subject administered an investigational drug that does not necessarily have a causal relationship with the treatment. An AE can therefore be any unfavorable and unintended sign (including an abnormal laboratory finding), symptom, or disease temporally associated with the use of the investigational product whether or not related to the investigational product. An AE is any sign, symptom, or diagnosis that appears or changes in intensity during the course of the study. An AE may be an intercurrent illness or an injury that impairs the well-being of the subject.

Severe hypoglycemia: Severe hypoglycemia is an event with one of the following symptoms: memory loss; confusion; uncontrollable behavior; irrational behavior; unusual difficulty in awakening; suspected seizure; seizure; loss of consciousness; or visual symptoms, in which the subject was unable to treat him/herself and which was associated with either a blood glucose level $< 54\text{ mg/dL}$ or prompt recovery after oral carbohydrate, IV glucose, or glucagon administration.

2. BACKGROUND AND RATIONALE:

2.1. BACKGROUND:

2.1.1. Total Pancreatectomy and islet autotransplantation (TP-IAT):

Chronic pancreatitis (CP) is a disease in which long-standing inflammation of the pancreas alters the normal structure and function (1). Approximately 15,000 Americans are diagnosed with CP each year. Recurrent bouts of pancreatitis result in inflammation, scarring, and blockage of the pancreatic ducts. These effects produce chronic pain that is difficult to control with medications. TP-IAT is currently being performed in around 20 centers worldwide and can effectively increase patients' quality of life and ameliorate post-operative diabetes in well-selected CP patients. A major hurdle in this procedure is that less than 30% of patients return to an insulin-independent state after TP-IAT, compared to a >85% diabetes-free rate before surgery. Compromised islet function is caused by pre-operative loss of beta cell mass from long-term inflammation within the diseased pancreas, but also by dramatic stress-induced islet cell death during harvest and post transplantation. Currently, no interventional protocols are in place to improve islet autograft survival and function in TP-IAT patients. Our long-term clinical research goal is to apply effective therapies that can facilitate islet cell survival and function to benefit patient care. These therapies are not only urgently needed for the prevention of post-surgical diabetes in CP patients, but can potentially serve as a powerful platform on which to investigate strategies for allogeneic islet cell transplantation for patients with T1D.

2.1.2. Alpha-1 antitrypsin (AAT)

AAT is a serine protease inhibitor that belongs to the serpin family. It has a high concentration in serum, and is available for clinical use as an affinity-purified human product (2). AAT inhibits various enzymes including neutrophil elastase, cathepsin G, proteinase-3, thrombin, trypsin, and chymotrypsin (3). Patients with a genetic deficiency in AAT exhibit 15-60% lower circulating AAT levels than normal and are prone to develop pulmonary emphysema (4). Besides inhibition of neutrophil elastase, AAT exerts anti-inflammatory effects via suppressing cytokine production, complement activation, and immune cell infiltration. AAT also functions as an anti-apoptotic factor for endothelial cells and vascular smooth muscle cells (5,6). AAT induces vascular endothelial growth factor (VEGF) expression and release, protects VEGF from proteolytic cleavage by elastase, promotes viability of endothelial cells, and enhances migration of myocytes. Recent studies indicated that AAT had profound beneficial effects in the treatment of diabetes. AAT protects β cells from apoptosis induced by pro-inflammatory cytokines and streptozotocin (7). A single injection of AAT to NOD mice reduced the intensity of insulitis, increased β cell mass, promoted β cell regeneration, and prevented the onset of diabetes via modulating T regulatory cells (8,9). AAT has been shown to protect islets from graft failure and immune rejection in mouse transplantation models with readily vascularized islet grafts (10,11). Adding AAT into ductal injection solution and collagenase solution improved porcine islet isolation by inhibiting trypsin activity during pancreas digestion (12). AAT monotherapy

elevates VEGF expression levels in islet allograft and prolongs islet allograft survival in mice via enhancement of intraislet VEGF expression and promotion of islet revascularization (11).

A recent study published by Koulmada and colleagues demonstrated that AAT treatment improved survival of islets after partial pancreatectomy and intrahepatic autologous islet transplantation in non-human primates (13). Thus, the beneficial effects of AAT in the islet transplantation setting may be mediated by its anti-apoptotic and anti-inflammatory properties and promotion of islet revascularization.

2.1.3. Clinical trials use of AAT for diseases:

Several clinical trials have been performed evaluating the effects of AAT in new onset diabetes. One trial entitled “A research trial of Aralast in new onset diabetes (RETAIIN)”, gave patients with new onset T1D AAT (Aralast NP) at 45mg/kg by intravenous infusion once a week for 6 weeks, and then a 3 week wash out, followed by a high dose of AAT at 90mg/kg for the next 6 weeks, with a total of 12 infusions. Data from this trial has yet to be published.

In another phase 1 open label trial in 12 new onset T1D patients treated with 80mg/kg of AAT weekly for 8 weeks, AAT led to increased, unchanged, or moderately reduced levels of C-peptide responses compared with baseline in 5 patients. No control group is available for comparison. In addition, mechanistic analyses revealed reduced levels of toll-like receptor-induced interleukin-1 β expression in monocytes and dendritic cells at 12 months post AAT treatment (14).

Most importantly, AAT has been used for the treatment of emphysema for more than 25 years with a remarkable record of safety (15), therefore it is an ideal candidate to be used in the islet transplantation setting to improve the efficacy of clinical islet transplantation.

2.2. RATIONALE:

2.2.1. Rationale for Selection of patient population:

Although the beneficial effects of AAT have been demonstrated in rodents and non-human primate islet transplantation models, its potential therapeutic effect has not been evaluated in patients with islet transplantation. We designed this randomized, double-blind, placebo control study to assess the safety and efficacy of 60 mg/kg of weekly IV injection of AAT in subjects with autologous islet transplantation. Unlike patients with type 1 diabetes, there is no recurrence of autoimmunity and immune rejection response in patients receiving autologous islets. Therefore, it is a suitable disease model to evaluate the protective effect of AAT to transplanted islets.

2.2.2. Rationale for the Selection of Dosing Regimen

AAT (Prolastin-C, Grifols) used in the current trial has been given a waiver for IND by the FDA.

Prolastin-C is indicated for chronic augmentation and maintenance therapy in adults with clinically evident emphysema due to severe congenital deficiency of AAT. The dosing regimen of Prolastin-C chosen for this study, 60 mg/kg given intravenously once per week, is the standard FDA-approved dosing regimen for emphysema, and is identical to other plasma-derived AAT products in the same class. At this dosage, Prolastin-C has been demonstrated to be safe and well tolerated in subjects with congenital AAT-deficiency, and was shown to increase and maintain circulating trough antigenic and functional AAT levels to 14.7 μ M (median; range: 11.6-18.5 μ M) and 11.9 μ M (median; range: 8.2-16.9 μ M), respectively (see Prolastin-c package insert).

2.2.3. Rationale for the Selection of Route of Administration and Infusion Rate

The route of administration (intravenous infusion), as well as the infusion rate (0.08ml/kg/min), selected for this study are in accordance with the FDA-approved package insert.

2.3. KNOWN AND POTENTIAL RISKS AND BENEFITS TO HUMAN PARTICIPANTS

2.3.1. General risks

Transplantation of islets is associated with several potential risks. These are intrinsic to the procedure and may result from the intrahepatic islet infusion as well as testing involved in the care and evaluation of transplanted subjects. All patients receiving TP-IAT are at risk of complication regardless of study participation.

2.3.2. Risks of use of Investigation product: Prolastin-C

Because clinical studies for Prolastin-C are conducted under widely varying conditions, adverse reaction rates observed cannot be directly compared to rates in other clinical trials and may not reflect the rates observed in practice. According to the Prolastin-C package insert, the most serious adverse reaction observed during clinical studies with Prolastin-C was an abdominal and extremity rash in one subject. The rash resolved subsequent to outpatient treatment with antihistamines and steroids. Two instances of a less severe, pruritic abdominal rash were observed upon re-challenge despite continued antihistamine and steroid treatment, which led to withdrawal of the subject from the trial.

The most common drug-related adverse reactions observed at a rate of $> 1\%$ in subjects receiving Prolastin-C were chills, malaise, headache, rash, hot flush and pruritus. Adverse reactions considered drug related by the investigators occurring in 1.6% of subjects (one subject each) treated with Prolastin-C were malaise, headache, rash, hot flush, and pruritus. Drug related chills occurred in 3.2% (2 subjects) of Prolastin-C subjects.

Products made from human plasma may carry a risk of transmitting infectious agents, e.g., viruses, and, theoretically, the Creutzfeldt-Jakob disease (CJD) agent. In each of 2 randomized, double-blind studies in which the predecessor product, PROLASTIN® (Alpha1-Proteinase Inhibitor [Human]), was compared to other AAT products, there was a single case of parvovirus

B19 seroconversion in the Prolastin-C arms of each trial. In each case, it could not be determined whether parvovirus had been acquired from Prolastin-C or from the community. However, during clinical studies with Prolastin-C, there were no reported treatment emergent cases of hepatitis B, hepatitis C, HIV or parvovirus B19 viral infections. Furthermore, the Prolastin-C process incorporates additional plasma safety and virus reduction measures that minimize the residual risk of virus transmission. Risk for placebo: patient may not be receiving a therapy as good as the alternative arm of the study. There is no other risk to placebo infusion at the dose provided.

2.3.3 Risks of blood sampling

In addition to the routine blood sampling, participation in the study will require an amount of blood higher than routine sampling at some time points, so that biomarkers of inflammation, chemokine/cytokines, and RNA expression can be measured. The risks of drawing blood include temporary discomfort from the needle stick, bruising and infection. Fainting could occur.

2.3.4. Other study related procedures

All other procedures including islet transplantation, c-peptide, and glucose testing are part of standard patient care and would be performed regardless of study participation.

2.4. POTENTIAL BENEFIT

2.4.1. Benefits to TP-IAT patients

There is no proven benefit to participants by entering this clinical trial. It is hoped that AAT treatment participants will have improved graft survival; however, this remains to be shown.

2.4.2. Benefits to society

This study may identify a useful medication that will benefit patients with islet transplantation.

3. OVERALL STUDY DESIGN AND PLAN DESCRIPTION:

3.1. STUDY DESIGN:

Experimental design: We propose to enroll a total of 48 CP patients who are scheduled for TP-IAT. This will be a 2:1 randomized, double blind, controlled study in which 32 patients receive islet cell transplantation together with intravenous AAT 60 mg/kg/week for 4 weeks, and 16 patients receive islets with intravenous 0.9% saline control in equivalent volume.

CP patients planning TP-IAT will receive an IRB approved consent form that describes the research study. Following signed consent, they will be enrolled and receive a baseline study visit. On the day of TP-IAT, an intravenous injection of AAT at the FDA approved dose of 60mg/kg or 0.9% normal saline will be infused before surgery. The autologous islet transplantation procedures will remain as routinely performed at MUSC. On the day of transplantation, the pancreas will be harvested and transferred to the Center for Cellular Therapy (CCT). Islets will be isolated and transplanted back to the patient via portal vein infusion. AAT or placebo will be given on day 0, 7, 14 and 21 days of islet transplantation.

3.2. STUDY TIME TABLE

Planned patients are expected to be recruited in a 36-month period. A follow-up of 12 months is planned for each patient. The overall timelines are as below:

- Projected starting date (first-patient-in): June 1, 2016
- Projected completion of patient accrual (last-patient-in): May 31, 2019
- Projected study end date: May 31, 2020

3.3. END OF STUDY

For this trial, end of the study is defined as the date of the last visit of the last patient.

3.4. STUDY OBJECTIVE

The objective of this clinical trial is to describe and compare the safety and efficacy of treatment with AAT in chronic pancreatitis patients who undergo TP-IAT.

3.5. STUDY ENDPOINTS:

3.5.1. Primary endpoint:

The primary endpoint will be Area under the curve for the serum C-peptide level during the first 4 hours of a mixed meal tolerance test (MMTT), normalized by the number of islet equivalents (IEQ)/kg at day 365±14 after islet transplant.

3.5.2. Secondary endpoints (measurements will be done at 365±14 days post-transplantation):

- Proportion of insulin-independent patients following IAT.
- Average daily insulin requirement.
- β cell function as assessed by β -score.

3.5.3. Exploratory endpoints

- Measurements of primary and secondary endpoints at day 75±14.
- Time course of instant blood mediated inflammatory reaction as measured by thrombin-anti-thrombin (TAT), C5a and c-peptide levels before, in the middle and after initiation of islet infusion, and 3h post islet infusion.
- Time course of inflammatory chemokines/cytokines as assessed by serum level of CXCL8, CCL2 (MCP-1), CCL3, CCL4, CXCL10 (IP-10), CXCL9 (MIG), IL-6, IL-10, INF- γ , TNF- α , and IL-1 β [pre-infusion, and 24, 72 and 168hrs, and day 14, and 21 after the end of islet infusion].
- Basal to 240 min time course of glucose, and C-peptide derived from the MMTT (day 75±14 to day 365±14).
- The proportion of patients with an HbA1c \leq 6.5% (day 365±14 days post-transplant only)
- Cumulative number of severe hypoglycemia events.
- The proportion of patients with an HbA1c \leq 6.5% at day 365±14 AND are free of severe hypoglycemic events from day 75±14 to day 365±14 inclusive.
- Daily oral Morphine Equivalents on day prior to visit (day 75±14 to day 365±14).
- Proportion of patients remaining on narcotics (day 75±14 to day 365±14).
- RNA expression profile in peripheral blood mononuclear cells (PBMCs) at 168 h post transplantation. RNA analysis will be done in at least 10 patients to guarantee post-treatment sampling in at least 3-4 patients randomized to AAT and 3-4 to control.
- SF-12 Quality of Life score

3.5.4. Safety endpoints:

- Incidence and severity of Adverse Events and Serious Adverse Events
- Standard laboratory tests including hematology (hematocrit, hemoglobin, red blood cells, platelets, white blood cells, differential white blood cell count), clinical chemistry (sodium, potassium, serum creatinine, blood urea nitrogen, total bilirubin, alanine aminotransferase (ALT), aspartate aminotransferase (AST) and coagulation (International Normalized Ratio (INR), partial thromboplastin time (PTT)), at pre-transplant hospital admission and post-transplant hospital

discharge].

- Vital signs, i.e. blood pressure (BP) and heart rate (HR) at pre-transplant hospital admission and post-transplant hospital discharge. ALT/AST, INR/PTT
- Weight loss from pre-transplant value [time frame: day 75±14 and 365±14 after the transplant]
- Serum level of albumin and pre-albumin (absolute and change from pre-transplant value) [time frame: day 75±14 and 365±14 after the transplant].
- Proportion of patients falling into one of the following levels of steatorrhea severity [time frame: day 75±14 and 365±14 after the transplant];
 1. No steatorrhea;
 2. Steatorrhea few times per week;
 3. Steatorrhea daily;
 4. Stool incontinence.
- Proportion of patients falling into one of the following malnutrition risk levels (poor prognosis, significant risk, increased risk, normal) according to pre-albumin level [time frame: day 75±14 and 365±14 after the transplant].
- Cumulative number of episodes of documented hypoglycemia (documented symptomatic; asymptomatic) [time frame: from day 75±14 to day 365±14 after the transplant].
- Cumulative number of diabetic ketoacidosis-related events [time frame: from day 75±14 to day 365±14 after the transplant].

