6.3. POST-OPERATIVE ASSESSMENTS

All routine measurements for TP-IAT patients will be measured according to current protocols for this patient population. SF-12 Quality of life and reduction in narcotic dose of morphine or equivalent will be obtained from the Islet Longitudinal Outcome Database (ILOD) which has granted this project authorization to use their information. . The following will be assessed during hospital stay and each time or when patients return for drug injection:

6.3.1. Instant blood mediated inflammatory reaction (IBMIR): 3ml of blood will be collected before AAT injection, before, in the middle, and after initiation of islet infusion and 3h post islet infusion. Serum will be collected and stored in -70 ° C for analysis of thrombin-anti-thrombin complex (TAT), C5a, and c-peptide level.

6.3.2. Chemokines/cytokines: A blood sample will be obtained at 0, 24, 72, and 168 h (before AAT injection), and day 14 (before AAT injection), and 21 (before AAT injection) post transplantation to measure chemokine and cytokine expression in the serum using the Lumix machine. Each time 5 ml of blood will be collected and centrifuged; aliquots of serum will be stored in in -70 ° C for further analysis.

6.3.3. DNA testing: A 10 ml whole blood sample will be collected during screening, and stored in -70 °C for isolation of genomic DNA for further analysis. This future analysis may be conducted by the PI or by other researchers who obtain IRB approval for their research. This research may involve genetic studies. The specimens will be labeled with a code that only study personnel can link back to the patient. Researchers outside of this study will not be given a link between the code number and patient's name or any other identifying information. We expect to store the specimens long-term for future studies on disease condition. Participant will not be contacted for additional consent. The investigators will not tell patient what they find out about the patient, nor will contact the patient if a test becomes available to diagnose a condition that a patient might have or later develop. Results will not be placed in the individual participant's medical record.

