8.2.1. MODIFIED INTENT-TO-TREAT POPULATION

The modified intent-to-treat (mITT) population includes all randomized subjects who meet study eligibility criteria and have received at least one injection (of AAT or placebo). The primary efficacy measures will be analyzed with the mITT population.

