8.11. SECONDARY EFFICACY ANALYSIS

A series of secondary efficacy and exploratory endpoints will be evaluated, as listed in Section 3.5.2 and 3.5.3. All secondary analyses will be conducted in an exploratory fashion with p-values and confidence intervals presented with no adjustments for multiple comparisons. Interval estimates will be generated at the 95% confidence level. Secondary analyses will be conducted on the mITT population and the per protocol population. Since most secondary endpoints will be collected at multiple time points for each participant, generalized linear mixed models will be utilized, as they are appropriate for longitudinal data analyses and can be adapted for binary dependent variables.

Secondary endpoints analyses are used to confirm or support the findings based on the primary outcome analysis. If most of the secondary endpoints show a change in the opposite direction

from the primary efficacy analysis or no direction, we might have less confidence in the primary endpoint.

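### The opioid endpoints are defined and analysed without the pre-surgery dose that section 6.3 implies is available, which costs precision and leaves the 'remaining on narcotics' denominator undefined

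*Combined protocol and SAP*

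**What the plan says.** Section 3.5.3 lists two opioid endpoints among the exploratory endpoints: "Daily oral Morphine Equivalents on day prior to visit (day 75±14 to day 365±14") and "Proportion of patients remaining on narcotics (day 75±14 to day 365±14"). Neither mentions a pre-surgery value, a change, or a restriction to patients who took narcotics before surgery.

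Section 6.3 states that "SF-12 Quality of life and reduction in narcotic dose of morphine or equivalent will be obtained from the Islet Longitudinal Outcome Database". A reduction needs a starting dose, but no endpoint in 3.5 and no analysis in section 8 uses it.

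Section 8.11 covers the endpoints of both 3.5.2 and 3.5.3 with generalized linear mixed models and names no baseline covariate. On the analysis set it says "Secondary analyses will be conducted on the mITT population and the per protocol population". Section 8.2.1 defines the mITT population as one that "includes all randomized subjects who meet study eligibility criteria and have received at least one injection (of AAT or placebo").

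SF-12 also comes from the outcome database. The synopsis lists it as a secondary endpoint ("Quality of life as measured by SF-12 questionnaire"). Section 3.5.2 omits it, and section 3.5.3 lists it as exploratory.

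**The concern.** The synopsis names pain relief and quality of life among the dimensions of efficacy. Section 3.5 lists no pain score, so the two opioid endpoints carry the pain-relief dimension. Follow-up dose is likely to depend on the dose before surgery. With a control arm of 16 and no stratification factor named in 8.4, leaving that dose out of the model keeps avoidable noise in the arm comparison. Section 8.3 intends the means, standard deviations and effect sizes from this trial to inform a larger one, so the noise would carry forward.

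The word 'remaining' raises a second problem. It makes sense for patients who were on narcotics before surgery, but the protocol does not say whether they alone form the denominator. Two analysts could report different proportions from the same data.

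**Working it through.** **The plan's own figure.** Section 8.3 claims 80% power for a 0.9 SD difference with 32 and 16 patients and up to 10% loss. After loss: 32 × 0.9 = 28.8 and 16 × 0.9 = 14.4. The standard error is √(1/28.8 + 1/14.4) = 0.323 SD, and 0.9/0.323 − 1.96 = 0.83, which gives 79.6% power (normal approximation, two-sided 5% assumed because no alpha is stated). The figure is reproduced. A t-test gives 77.7%.

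**Does any other provision bring in the pre-surgery dose?**
- 8.4: permuted blocks at 2:1, with no stratification factor named.
- 8.8: the baseline characteristics given do not include opioid use.
- 8.9: the only covariate rule is triggered by a significant difference between study subjects and historical controls. An AAT–placebo imbalance does not trigger it.
- Appendix 1: no row for opioid use or SF-12.

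By contrast, the safety endpoints in 3.5.4 include "Serum level of albumin and pre-albumin (absolute and change from pre-transplant value"), and the example model in 8.12 carries the baseline value as a covariate. The plan therefore uses baseline values elsewhere.

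**Precision.** In whole patients the evaluable arms are about 29 and 14, assuming the 10% loss in 8.3 also applies to these endpoints. In SD units of the follow-up value:

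- unadjusted: √(1/29 + 1/14) = 0.325
- adjusted for baseline: 0.325 × √(1 − r²)
- simple change score: 0.325 × √(2(1 − r))

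Here r is the baseline–follow-up correlation. The documents do not give it, so a range is shown. The formulas assume equal SDs at both times and a linear relation, and ignore the degree of freedom spent on the covariate. Power is for 0.9 SD by t-test at 28.8/14.4.

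| r (assumed) | SE unadjusted | SE adjusted | SE change score | Power unadjusted | Power adjusted | Power change score |
|---|---|---|---|---|---|---|
| 0.3 | 0.325 | 0.310 | 0.385 | 77.7% | 81.4% | 63.4% |
| 0.5 | 0.325 | 0.282 | 0.325 | 77.7% | 88.2% | 77.7% |
| 0.7 | 0.325 | 0.232 | 0.252 | 77.7% | 96.8% | 94.0% |

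For r of 0.5–0.7 adjustment cuts the standard error by 13–29%. The change score is worse than the unadjusted dose below r = 0.5.

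**Denominator.** Let q be the share of patients not on narcotics before surgery, and suppose none of them starts afterwards. A difference between arms among users is then multiplied by (1 − q) when everyone is in the denominator. If 60% and 30% of users remained on narcotics (assumed), the 30-point difference would read as 27, 24, 21 or 18 points for q = 10, 20, 30 or 40% (assumed). The two denominators answer different questions, so the plan must state which it means.

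**The case against.** A reader might infer that the protocol counts patients who never took narcotics as successes. No section says so. One can only remain on something already being taken, so a denominator of prior users is a natural reading. What stands is that the denominator is unstated, and that the default mITT and per-protocol sets would include any patient not on narcotics before surgery.

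A reader might also infer that the comparison is biased because one arm could start with fewer users or lower doses. Under randomization such differences are due to chance, and the standard error of an unadjusted comparison already allows for them. The loss is in precision.

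Nor does the protocol disregard earlier use altogether, since 6.3 plans to obtain a reduction. The gap is that 3.5.3 and 8.11 do not use it. That 6.3 refers to a pre-surgery dose, and that this dose can be extracted for every patient, is inferred from the word 'reduction' and is not stated.

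Two further points stand. If many follow-up doses are zero, the linear formula is only a rough guide to the gain. And 8.3 calls all hypothesis testing exploratory, so no confirmatory claim depends on these endpoints.

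**Conclusion.** The point holds as a minor one. Both opioid endpoints are defined from follow-up alone and 8.11 names no baseline covariate, although 6.3 implies that a pre-surgery dose is available. Adjusting for it would lower the standard error of the arm difference from 0.325 to about 0.28–0.23 SD. This rests on an assumed correlation of 0.5–0.7, about 29 and 14 evaluable patients, and a linear approximation. The denominator of the proportion needs a definition.

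The SF-12 tier conflict is real but changes no analysis, because 8.11 treats the endpoints of 3.5.2 and 3.5.3 alike, without multiplicity adjustment. It affects whether SF-12 falls under the promise in 8.9 to report all primary and secondary outcomes, and whether it counts among the secondary endpoints that 8.11 weighs against the primary result. The primary analysis and the sample size are unaffected.

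**What to change.** - In 8.11, analyse daily morphine equivalents at day 75 and day 365 with the pre-surgery daily dose as a covariate, not as a simple change score. Do the same for SF-12 where a pre-surgery score exists.
- In 3.5.3, report the proportion on narcotics at follow-up among patients taking them before surgery, and also among all patients so that new use after surgery is kept.
- Have the sponsor confirm that the database holds a pre-surgery dose and SF-12 score for trial patients, and state the date to which each refers.
- List SF-12 in the same tier in the synopsis and in section 3.5.

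The cost is protocol and SAP wording, plus extraction of the pre-surgery values from a database the project is already authorised to use, if it holds them. The downside is a smaller denominator for the proportion among pre-surgery users.
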